### 5. KNOWN AND POTENTIAL RISKS AND BENEFITS TO PARTICIPANTS

# 5.1 RISKS OF INVESTIGATIONAL DRUG AS CITED IN INVESTIGATOR'S BROCHURE

Precautions for hypersensitivity events are required. Hypersensitivity events such as injection site reaction (13.3%), injection site pain (2%), rash (4.7%), and eczema (3.1%) were reported in individuals receiving AMG 714.  All hypersensitivity reactions were mild and transient. There are no reports of anaphylaxis to AMG 714. All individuals who receive AMG 714 or AMG 714 placebo will be monitored for 1 hour after injection to detect any possible injection site reaction, hypersensitivity, and/or anaphylactic reaction (Section 6.1.3.4). AMG 714 is contraindicated in individuals with a known sensitivity to proteins derived from mammalian cell lines or other components of this drug.

The effect of AMG 714 on pregnancy, breast-feeding, pediatric participants, or geriatric participants is not known. No clinical studies have been conducted in individuals with renal or hepatic impairment. The effects of an overdose of AMG 714 are not known, and an antidote is not available. There is no evidence that AMG 714 use is habit forming.

## 5.2 RISKS OF INVESTIGATIONAL DRUG CITED IN MEDICAL LITERATURE

The results of study Hx-IL15-001 with AMG 714 in rheumatoid arthritis have been published. Related adverse events reported in this study (n=30) include influenza-like symptoms, transient pyrexia, myalgia, injection site reactions, upper respiratory site infection (managed with antibiotics), herpes simplex virus, and aphthous stomatitis. None were

moderate or severe. In addition, fluorescence-activated cell sorting for T cell and NK cell subsets did not show significant changes from baseline up to 28 days after treatment.

### 5.3 RISKS OF OTHER PROTOCOL SPECIFIED MEDICATIONS

There are no other protocol specified medications.

#### 5.4 RISKS OF STUDY PROCEDURES

The risks of the study procedures are as follows:

- 1. Study drug administration: Injection site reactions such as pain, redness, or swelling at the injection site are common.
- 2. Blood draw: Low risk of hemorrhage, hematoma, or infection at the venipuncture site.
- 3. Skin biopsies: Low risk of hemorrhage, hematoma or infection at the biopsy site. Scarring at the biopsy site is expected, however the biopsy diameter will be small and every effort will be made to collect biopsies from non-exposed areas of the body.
- 4. Narrow band UVB phototherapy: Low risk of erythema, xerosis, pruritus, folliculitis, sunlight-induced rash, or worsening of vitiligo.
- 5. Questionnaires: Low risk of discomfort due to questions that may be sensitive in nature.

### 5.5 RISK OF SARS-COV-2

Participants will be educated and advised about the importance of adherence to recommendations of the Center for Disease Control and Prevention (CDC) and other public health authorities for reducing the risk of SARS-CoV-2 infection, including vaccination.

## 5.6 POTENTIAL BENEFITS

The overall goal of this study is to examine whether inhibition of the IL-15 pathway can induce immune tolerance in vitiligo by depleting autoreactive T-cells, leading to the repigmentation of vitiligo lesions. Participants themselves may not directly benefit from the trial since the active study medication may not be an effective treatment for vitiligo. In addition, some participants will receive placebo instead of active study medication. However, the insight gained from studying the clinical efficacy of IL-15 blockade in the treatment of vitiligo may improve the understanding of the pathogenesis of vitiligo and help identify novel therapeutic targets for future study. All participants whose T-VASI score does not improve by at least 25% by Week 24 will undergo 24 weeks of nbUVB phototherapy, a standard treatment for vitiligo.

## 6. INVESTIGATIONAL DRUG

### 6.1 INVESTIGATIONAL DRUG

#### 6.1.1 AMG 714

AMG 714 is the investigational drug used in the study and will be given at a dose of 300 mg SQ every 2 weeks for a total of 6 doses. AMG 714 is not FDA-approved and is in clinical development by Amgen.

Each sterile 10 cc vial of AMG 714 is filled with a 2 mL deliverable volume of 100 mg/mL AMG 714 formulated in 10 mM sodium acetate, 9.0% w/v sucrose, and 0.004% w/v polysorbate 20, pH 5.2. AMG 714 is stored as a frozen liquid at  $\leq$  -30°C  $\pm$  10°C and protected from light.

## 6.1.2 AMG 714 Placebo

The AMG 714 placebo used in clinical trials contains the same liquid formulation as AMG 714. Each sterile vial of AMG 714 placebo contains 1 ml volume of 10 mM sodium acetate, 9% w/v sucrose, and 0.004% w/v polysorbate 20, pH 5.2 without the active ingredient. The placebo solution is not visually distinguishable from AMG 714.

AMG 714 placebo is stored in the same fashion as AMG 714.

# 6.1.3 Dosage, Preparation, Administration, and Treatment of Hypersensitivity or Anaphylaxis

### 6.1.3.1 Dosage

The dose of AMG 714 to be used in this study is 300 mg every 2 weeks for a total of 6 doses. Each dose will be administered as 2 subcutaneous (SQ) injections (1.5 mL each). Placebo will also be administered as 2 SQ injections (1.5 mL each).

## 6.1.3.2 Preparation

Doses of AMG 714 or placebo will be prepared by the unblinded study site PoR according to the investigational pharmacy manual. After preparation, AMG 714 or placebo may be stored for up to 72 hours at 2-8°C, and no longer than 12 hours at room temperature. Prolonged exposure to light during storage should be avoided.

AMG 714 should be warmed to room temperature for a minimum of 1 hour before administration. Light exposure should continue to be avoided. The syringe should be inspected by the study staff member responsible for administering study drug for any visible foreign particles. If the study drug is not suitable for injection, it should be returned to the unblinded study PoR and replaced.

#### 6.1.3.3 Administration

Temperature, blood pressure, pulse and respirations will be obtained immediately before study drug administration and 60 minutes after study drug administration. Study participants will be monitored for 1 hour after study drug administration to detect any possible injection site reaction, hypersensitivity, and/or anaphylaxis (Section 6.1.3.4).

AMG 714 or placebo will be administered subcutaneously by trained health care staff not otherwise involved in the vitiligo assessment of the participant (Section 3.5.1). Each dose will be comprised of two separate syringes, each containing 1.5 ml of AMG 714 or placebo. The SQ injections should be administered on the participant's anterior abdominal wall in a consecutive fashion approximately 2 cm apart. The side of the abdominal wall should be alternated at every visit (i.e., left side at one visit, right side at the next visit).

If more than one participant is scheduled to receive study drug on the same day at the same investigational site, at least 15 minutes must elapse between study drug administration to each participant.

### 6.1.3.4 Treatment of Hypersensitivity and/or Anaphylaxis

Participants will be monitored as specified in Section 6.1.3.3 for 1 hour after administration of the study treatment for hypersensitivity and anaphylaxis reactions. Administration of AMG 714 or placebo will be stopped immediately if any of the following hypersensitivity/anaphylaxis reactions occurs (Table 3 Section 12.3.1):

- Any grade 2 or higher hypersensitivity/anaphylaxis reaction, or
- A generalized pruritus or urticaria grade 1 hypersensitivity/anaphylaxis reaction.

Appropriate treatment for the reaction per institution's guidance will be instituted. Appropriate treatment may include corticosteroids, antihistamines, epinephrine, bronchodilators, or oxygen.

All participants should be instructed to seek immediate medical attention if they experience any delayed onset hypersensitivity or anaphylaxis symptoms as listed in Table 3 (Section 12.3.1).

### 6.2 DRUG ACCOUNTABILITY

Under Title 21 of the Code of Federal Regulations (21CFR §312.62) the investigator is required to maintain adequate records of all investigational drug storage and disposition. For all DAIT-sponsored clinical trials, these responsibilities are delegated to the site's PoR. The PoR must maintain all records related to storage and disposition of AMG 714 active and placebo vials including:

- 1. Ensure drugs are stored in a secured area, with access limited to authorized pharmacy personnel and stored under appropriate temperature range as specified in the protocol and pharmacy manual.
- 2. Date and quantity of the drug received.
- 3. Date and quantity of the drug dispensed.
  - a. A drug dispensing log will be kept current for each drug and participant. These logs will contain the drug information, identification of each participant, the date, and quantity of drug dispensed. Please see pharmacy manual for more detailed information.
- 4. Detailed accountability of any unused (un-dispensed) AMG 714 active and placebo vials for return to DAIT/NIAID investigational drug distributor.
  - a. All remaining unused and/or expired AMG 714 active and placebo vials will be returned to DAIT/NIAID investigational drug distributor during study and after study termination.

All records regarding drug disposition will be maintained by the study site's investigational pharmacy and available for inspection.

# 6.3 ASSESSMENT OF PARTICIPANT COMPLIANCE WITH INVESTIGATIONAL DRUG

Study treatment will be administered by trained health care staff. Compliance, therefore, will be monitored by the site and documented on the eCRF.

#### 6.4 TOXICITY PREVENTION AND MANAGEMENT

Study treatment must be suspended if the participant develops an infection or other AE that the investigator judges to be significant. Study treatment must be suspended if the participant develops a confirmed SARS-CoV-2 infection.

If the infection or AE resolves, AMG 714 or placebo may be restarted at the next scheduled dose.

Clinically significant laboratory abnormalities should be repeated within 48 hours of awareness.

#### 6.4.1 Hypersensitivity or Anaphylaxis

Administration of AMG 714 or placebo will be permanently discontinued if the participant develops a hypersensitivity/anaphylactic reaction, as described in section 6.1.3.4.

## 6.4.2 Liver Chemistry Abnormalities

Participants will be monitored for drug induced liver injury. The recommended dose modifications for elevations in ALT and AST are summarized in Table 1.

**Table 1. Dose Modification for Liver Chemistry Abnormalities** 

ALT/AST	Action
≤ 3xULN	Maintain dose
$>3xULN$ to $\le 5xULN$ with serum total bilirubin $\le 2x$	Suspend AMG 714 or placebo.
ULN	Resume AMG 714 or AMG 714 placebo at the next expected dose if ALT and AST decrease to ≤3xULN.
	If AMG 714 or AMG 714 placebo is resumed, permanently discontinue AMG 714 or placebo if ALT or AST increases to >3xULN a second time.
>3xULN with serum total bilirubin > 2xULN (Hy's Law)	Discontinue AMG 714 or placebo
> 5xULN	Discontinue AMG 714 or placebo

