#### 8.6 UNSCHEDULED VISITS

If disease activity increases or other concerns arise between regularly scheduled visits, participants should contact study personnel and may be asked to return to the study site for an "unscheduled" visit to assess vitiligo disease activity or adverse events. Assessments obtained during an unscheduled visit are outlined in Appendix 1. Some assessments for an unscheduled visit may be omitted at the discretion of the investigator if not indicated.

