#### 8.7 VISIT WINDOWS

Study visits should take place within the time limits specified in Table 2. Visit 0 must occur within 28 days of Visit -1. All other scheduled study visits must occur within the time limits specified in Table 2.

Table 2. Visit Windows

Visit	Timepoint	Visit Window				
Screening: Visit -1	Within 28 days of Day 0					
Baseline: Visit 0	Day 0	n/a				
Visits 1 to 6	Every 2 weeks through week 12	+/- 3 days				
Visits 7 to 10	Weeks 18, 24, 36, and 48	+/- 7 days				

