# 12.3.2 Grading of Liver Chemistry Abnormalities

For this study, liver function abnormalities will be graded using protocol specific criteria, and are defined relative to the upper limit of normal (ULN) as follows:

- Aspartate aminotransferase [AST] increased
  - o Grade 1: > ULN 3.0x ULN
  - $\circ$  Grade 2: > 3.0x ULN 5.0x ULN
  - o Grade 3: > 5.0x ULN 20.0x ULN
  - $\circ$  Grade 4: > 20.0x ULN
- Alanine aminotransferase [ALT] increased

- o Grade 1: > ULN 3.0x ULN
- $\circ$  Grade 2: > 3.0x ULN 5.0x ULN
- o Grade 3: > 5.0x ULN 20.0x ULN
- o Grade 4: > 20.0x ULN
- Alkaline phosphatase [ALP] increased
  - o Grade 1: > ULN 2.5x ULN
  - o Grade 2: > 2.5x ULN 5.0x ULN
  - o Grade 3: > 5.0x ULN 20.0x ULN
  - $\circ$  Grade 4: > 20.0x ULN
- Blood bilirubin increased
  - o Grade 1: > ULN 1.5x ULN
  - o Grade 2: > 1.5x ULN 3.0x ULN
  - o Grade 3: > 3.0x ULN 10.0x ULN
  - o Grade 4: > 10.0x ULN

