#### 12.4.3 Recording Adverse Events

Grade 2 or higher AEs will be recorded on the appropriate AE case report form (eCRF) for this study. A generalized pruritus or urticaria Grade 1 hypersensitivity/anaphylaxis reaction,

or confirmed Grade 1 SARS-CoV-2 infection will also be recorded (Section 6.1.3.4). The investigator will record these adverse events and serious adverse events (Section 12.2) on the appropriate AE/SAE eCRF regardless of the relationship to study treatment or study procedure.

Once recorded, an AE/SAE will be followed until it resolves with or without sequelae, or until the end of study participation, or until 30 days after the participant prematurely withdraws (without withdrawing consent) or is withdrawn from the study, whichever occurs first.

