#### **APPENDIX 1. SCHEDULE OF EVENTS**

Phase of Trial	SCRN			Do	sing				Post-t	reatme	ent (FU	) 	WD 	UN 
Week		0	2	4	6	8	10	12	18	24	36	48	WD	U
Visit 	V-1	V0	V1	V2	V3	V4	V5	V6	V7 	V8	V9	V10	WD	U
	G	ENE	RAL	ASSE	SSMI	ENTS								
Informed consent	X													
Eligibility criteria	X													
Randomization 		X												
Medical history & demographics	X													
Vitiligo history	X													
Concomitant medications	X	X	X	X	X	X	X	X	X	X	X	X	X	X
Comprehensive physical examination	X							X		X		X	X	
Limited physical examination		X	X	X	X	X	X				X			X
Vital signs	X	X	X	X	X	X	X	X		X	X	X	Х	X
Adverse events	X	X	X	X	X	X	X	X	X	X	X	X	Х	X
Treatment Assignment Survey								X					Х	
	STUE	Y DI	RUGA	ADMI	NIST	RAT	ION							
Study drug (AMG 714 or placebo)		X	X	X	X	X	X							
		PI	ЮТО	THE	RAPY	Z .	 	 	 		 		 	
nbUVB phototherapy 										X	X	X		

Protocol ITN086AI: REVEAL Evaluation of AMG 714 for Vitiligo

<sup>1 After Week 12, remote follow-up contact will occur at least once between each visit to facilitate participant retention, and to discuss phototherapy in participants receiving this treatment after Week 24.

<sup>2 See Sections 11.2 and 11.4 for additional information related to the early study withdrawal visit.

<sup>3 Some assessments for an unscheduled visit may be omitted at the discretion of the principal investigator if not indicated.

<sup>4 Remote visit allowable if indicated at V1, V2, V4, and V5.

<sup>5 V7 will be conducted as a telephone visit (Section 8.4).

<sup>6 Randomization must occur at least one day prior to V0.

<sup>7 Participants will undergo narrow band ultraviolet B (nbUVB) phototherapy if T-VASI does not improve by  $\geq$  25% at Week 24 compared to Week 0.

Phase of Trial	SCRN	Dosing Post-treatment (FU) 				) 	WD 	UN 						
Week		0	2	4	6	8	10	12	18	24	36	48	WD	U
Visit 	V-1	V0	V1	V2	V3	V4	V5	V6	V7 	V8	V9	V10	WD	U
	CLINICA	L LA	BOR	ATOR	YAS	SESS	MEN	TS						
Hematology (CBC w/diff and plt)	X	X			X			X		X	X	X	X	X
Chemistry (Cr, T bili, AST, ALT, ALP, albumin)	Х	x			X			X		X	X	X	X	x
TSH	X													
HIV	X													
Hepatitis B (core Ab & surface Ag)	X													

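### After a Week 6 ALT/AST rise and resumption at Week 8, no liver test is required between the resumed dose and the Week 10 dose, so Table 1's second-rise stop depends on discretionary testing

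*Combined protocol and SAP*

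**What the plan says.** Section 6.4.2 states: "Participants will be monitored for drug induced liver injury". It gives no test interval and refers to Table 1 for dose modification. In the row for ALT or AST above 3 and up to 5 times ULN with total bilirubin no more than twice ULN, drug is suspended. It may restart at the next expected dose once both enzymes have fallen to 3 times ULN or less. The row ends with the instruction to "permanently discontinue AMG 714 or placebo if ALT or AST increases to >3xULN a second time". Section 6.4.2 describes the Table 1 modifications as recommended, but Section 6.5 item 7 lists liver abnormalities meeting Table 1 among the reasons for which drug will be permanently stopped. The second-rise stop is therefore binding.

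Appendix 1 places doses at Weeks 0, 2, 4, 6, 8 and 10. The chemistry panel, which includes ALT, AST and total bilirubin, is marked at screening and Weeks 0, 6, 12, 24, 36 and 48, and at withdrawal and unscheduled visits. Weeks 8 and 10 are blank. Table 2 in Section 8.7 sets Visits 1 to 6 at "Every 2 weeks through week 12", each with a window of 3 days either side. A footnote to Appendix 1 allows the Week 8 and Week 10 visits to be remote.

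**The concern.** A stopping rule works only if the measurement that triggers it is taken in time. Week 6 is the only scheduled chemistry after the first dose and before the last, so it is the main scheduled route into the suspend-and-resume row. Participants who resume have already shown one liver signal on blinded drug, and the second-rise stop is the safeguard written for them. If no test is required between the resumed dose and the last dose, a site can meet every written requirement and still give the Week 10 dose to someone whom the rule would have stopped. What is at stake is participant safety and whether the rule can operate. The primary analysis is not affected.

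**Working it through.** The plan states no figure to reproduce. The check sets the dosing and chemistry rows side by side and then looks for any other text that would require a test.

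**Step 1: schedule (Appendix 1).**

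| Visit | Nominal day | Dose | Scheduled chemistry |
|---|---|---|---|
| Week 6 | 42 | Yes | Yes |
| Week 8 | 56 | Yes | No |
| Week 10 | 70 | Yes (last) | No |
| Week 12 | 84 | No | Yes |

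**Step 2: doses the stop could still withhold after a first rise found at Week 6.**
- Resume at Week 8: one dose remains (Week 10). Scheduled chemistry after day 56 and up to day 70: none.
- Resume at Week 10: no dose remains.

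The exposure is therefore at most 1 of 6 doses.

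**Step 3: intervals.** Interval = later day − earlier day. Each visit may move 3 days either way (Table 2), so an interval between two visits may move by 3 + 3 = 6 days.
- Week 8 to Week 10: 70 − 56 = 14 days (8 to 20). This is the minimum age, at the Week 10 dose, of the newest required ALT/AST result, because that result predates the resumed dose.
- Week 8 to Week 12: 84 − 56 = 28 days (22 to 34), from the resumed dose to the next required chemistry.
- Week 10 to Week 12: 84 − 70 = 14 days (8 to 20), from the last dose to that chemistry.

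**Step 4: other text that might require the missing test.**
- *Resumption condition, Table 1.* It implies a test showing both enzymes at 3 times ULN or less, but that test comes before the Week 8 dose.
- *Section 6.4.* "Clinically significant laboratory abnormalities should be repeated within 48 hours of awareness". This follows an abnormal result already in hand. Applied to the Week 6 result, it too precedes resumption.
- *Section 6.4.2.* Monitoring for liver injury is promised, with no test or interval.
- *Section 12.4.3.* "Once recorded, an AE/SAE will be followed until it resolves with or without sequelae". Under Section 12.3.2, where "liver function abnormalities will be graded using protocol specific criteria", the first rise is Grade 2, and a value above ULN and up to 3 times ULN is Grade 1. If values are still raised at resumption, follow-up may prompt a retest, though no interval is set. If values have normalised and the event is closed, it prompts nothing.
- *Section 8.6.* "Some assessments for an unscheduled visit may be omitted at the discretion of the investigator if not indicated". Chemistry is available at such a visit, but no text requires the visit.

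The number of liver tests required between the resumed Week 8 dose and the Week 10 dose is zero.

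**The case against.** The strongest reply is that monitoring is promised and only its interval is left to clinical judgement. The first rise is a recorded Grade 2 event under follow-up. Unscheduled chemistry may be left out only when not indicated. Investigators must suspend for any adverse event they judge significant, and may stop drug in the participant's interest (Section 6.5 item 8). Many would retest. The path is also narrow: the rise must stay within one row of Table 1, recover by Week 8, and recur before Week 10. The listed drug risks in Section 5.1 include no liver toxicity. The one hepatitis serious adverse event in Section 1.4.1 occurred at 8 mg/kg and was not assessed as related. All of this stands, and it limits the size of the point. It does not supply a required test after resumption.

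Three stronger readings are tempting, and the documents do not support them.
- A reader might infer that no liver test at all is required before Week 10. Table 1's condition for resuming implies one before Week 8, and Section 6.4 calls for a 48-hour repeat of a clinically significant abnormality. The gap begins after the resumed dose.
- A reader might infer that every resumption lacks a later scheduled test. A first rise found by unscheduled testing before Week 6 could have its second rise caught at the scheduled Week 6 draw.
- A reader might infer from Section 6.5 item 3b, which asks for repeat testing before the next dose, that hematology has a safeguard withheld from liver tests. That item confirms an abnormality already found, as one of three conditions for stopping. It is not surveillance after resumption.

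**Conclusion.** The point holds for one path: a first rise above 3 and up to 5 times ULN (bilirubin no more than twice ULN) found at the scheduled Week 6 draw, with dosing resumed at Week 8. On that path no required test can trigger the binding second-rise stop in time to withhold the Week 10 dose, and the rule acts only through discretionary testing. The gap is clearest when values had normalised and the event was closed before resumption.

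The size is small: at most one dose of six. The documents give no rate of ALT or AST above 3 times ULN, so the number of participants is not estimated; it is expected to be few. The conclusion concerns what the text requires, not what careful sites would do, and the day counts assume visits within the Table 2 windows. It is worth correcting because the rule is the plan's own, the consequence concerns safety, and the remedy is cheap.

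**What to change.** Add to the Table 1 row for ALT/AST above 3 and up to 5 times ULN, with a matching footnote on the chemistry row of Appendix 1: a participant who resumes after this suspension must have ALT, AST and total bilirubin drawn after the resumed dose and resulted before the next dose. The same applies before any later dose not already preceded by a scheduled chemistry result. A local laboratory is acceptable if the visit is remote.

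The cost is one extra routine draw on the Week 6 to Week 8 path, and up to a few if resumption comes earlier after an unscheduled finding. A planned remote visit may have to be in person, and the dose may have to wait briefly for the result. The visit window is only 3 days either side, so turnaround should be arranged in advance: a late result could cost a dose, and the per-protocol sample requires at least 5 of 6. The panel is already in the trial, and no endpoint, sample size or blinding arrangement changes.
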